**Table 1. BCX1812-306: Schedule of Assessments**

Assessments	Screening 	Baseline  (Pre-dose)	Day 1 Treatment Day 	Day 3	Day 7 (+ 2 days)	Day 14 (+ 3 days) / End of Study	Early Withdrawal
Informed Consent	X						
Inclusion/Exclusion Criteria	X						
Medical History/Physical Exam	X			X 	X 		
Vital Signs 	X			X	X	X	X
Body Temperature 	X	X	X	X	X	X	X
Clinical Chemistries and Hematology 		X			X		X
Urinalysis 		X			X		X
Pregnancy Test (Urine or Serum)	X					X	X
Assessment of influenza symptoms 	X		X	X	X	X	X
Ability to Perform Usual Daily Activities 		X		X	X	X	X
Influenza Related Complications (IRC) 	X			X 	X	X	X
Concomitant Medications Review	X		X	X	X	X	X
Subject Diary Review			X	X	X	X	X
Pharmacokinetic (PK) Sampling			X				
Serum sample for influenza antibody analysis 		X		X	X		X
Swabs for Virology Analysis		X		X	X		X
Rapid antigen test (RAT) or FDA- approved PCR test for influenza A and B on nasal specimen	X						

Assessments	Screening	Baseline (Pre-dose)	Day 1 Treatment Day	Day 3	Day 7 (+ 2 days)	Day 14 (+ 3 days) / End of Study	Early Withdrawal
Study Drug Administration			X				
Adverse Events 	X	X	X	X	X	X	X

- 1 It is expected that the date of Screening, Baseline, and Day 1 (date of study drug administration) will be the same. Day 1 consists of pre and post-dose assessments.
- 2 Vital sign measures will include blood pressure, pulse rate, and respiration rate. Vital signs will be recorded once during Screening, and vital signs will be taken once on remaining study visit days.
- 3 The investigator will record oral body temperature at Screening. Thereafter, the subject or care giver will record oral body temperature approximately every 12 hours in the Subject Diary until temperature normalizes for 48 hours (i.e. temperature without antipyretic is < 37.4°C/ 99.4°F orally for 4 measurements).
- 4 Clinical laboratory assessments performed at Screening are for the purpose of establishing a baseline. Subjects may be enrolled and begin treatment with study drug prior to receiving results. These labs may be done at any visit if necessary for patient management or adverse event monitoring purposes.

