##### **9.9.1. Antipyretics and Analgesics**

Resolution of fever is an important efficacy endpoint for this study. Accordingly, use of any antipyretics or analgesics with antipyretic properties must be carefully controlled and documented. Antipyretics and analgesics may be administered while the subject is enrolled in this study. The names and times of administration of these medications will be recorded by the subject/caregiver in the subject diary. To avoid the confounding effects of antipyretic medications, temperature measurements recorded by the subjects will be taken, whenever possible, at least 4 hours after administration of the antipyretic medication.

Continuation of low dose aspirin for cardioprophylaxis is allowed.

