##### **10.1.2.2. Day 1/Post-dose**

The following procedures/evaluations will be performed post-dose on Day 1:

- Collect up to 3 plasma samples, where possible, during the following time periods, beginning from the end of dosing until release from the site. For each plasma sample the calendar date and 24-hour clock time of sample collection will be recorded:
  - One time point immediately following completion of the infusion
  - One time point from 30 minutes to 1 hour post-infusion
  - One time point from 1 hour to 3 hours post-infusion
- Train the subject/caregiver on the recording of the following in the subject diary:
  - Subject's body temperature, obtained at approximately 12-hour intervals each day until the temperature normalizes for 48 hours (and 4 hours from last antipyretic medication administration or immediately prior to administration).

- Instruct the subject to assess his/her time lost from work, if applicable, and the recording of the subject's ability to perform usual daily activities using a 0 to 10 visual analogue scale.
- Assessment of signs and symptoms of influenza twice daily beginning on Day 1 (see Section [10.2.2](#)).
- Review and record concomitant medications
- Obtain and record body temperature
- Review and record AEs

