#### **10.2.1. Body Temperature**

The Investigator will record oral body temperature at Screening. The baseline temperature will be recorded at the Day 1 visit prior to dosing, regardless of whether the subject had recently taken an antipyretic. Thereafter, the subject or caregiver will record oral body temperatures approximately every 12 hours through Day 14 in the subject diary. Subjects or caregivers will measure their oral temperature with an electronic thermometer (provided by the Sponsor for the study). With the exception of the

baseline measurement, subjects will be instructed to take all temperature measurements at least 4 hours after, or immediately before, administration of oral acetaminophen or other antipyretic medications. The times of each temperature determination will be recorded in the Subject Diary.

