Up to 3 blood samples will be drawn to obtain plasma samples for drug concentration determinations, where possible, during the following time periods, beginning from the end of dosing until release from the site on the day of dosing:

- One time point immediately following completion of the infusion
- One time point from 30 minutes to 1 hour post-infusion
- One time point from 1 hour to 3 hours post-infusion

AEs and concomitant medications will be monitored at each scheduled visit from the Screening assessment to final study visit. Clinical laboratory investigations (chemistries, hematology, and urinalysis) will be collected at Baseline, Day 7, and Early Withdrawal visits. Safety and tolerability will be evaluated through assessments of AEs, laboratory analyses (clinical chemistry, hematology, and urinalysis), vital signs, and physical examinations at the time points indicated in the schedule of assessments (see Section 1.2).

All subjects or their caregivers will record the following information in a Subject Diary:

- Assessment of the presence and severity of each of 7 symptoms of influenza on a 4-point severity scale (0, absent; 1, mild; 2, moderate; 3, severe) at Screening, then twice daily through Day 13, and prior to the subject's clinic visit on Day 14 or until each symptom is rated as a 0 or 1 for 48 consecutive hours. Diaries will be reviewed at each clinic visit.
- Temperature measurements (oral) will be taken with an electronic thermometer provided by the Sponsor, approximately every 12 hours until temperature normalizes for 48 hours (ie, temperature without antipyretic is $< 37.4^{\circ}\text{C}/99.4^{\circ}\text{F}$ orally for 4 consecutive measurements). With the exception of the Screening/ Baseline measurement, all temperature measurements will be obtained at least 4 hours after, or immediately before, administration of oral acetaminophen or other antipyretic medications, if taken.
- The type, date, and time of medications used for the symptomatic treatment of influenza-related symptoms.
- Assessment of the subject's ability to perform usual activities using a 0 to 10 visual analog scale once daily through Day 14, where 0 = Unable to perform usual activities at all, and 10 = Able to perform all usual activities fully.

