5.2.2. Effectiveness Analyses

A subject's oral temperature taken by subjects and recorded in the diary by subjects/caregivers will be summarized by age group and overall by study visit. A subject has Resolution of Fever if he/she has an oral temperature $< 37.4^{\circ}\text{C}/99.4^{\circ}\text{F}$ oral and no antipyretic medications have been taken for at least 12 hours. The time to resolution of fever will be estimated for each age group and overall using the Kaplan-Meier method with temperature and symptom relief medication information obtained from the subject diary data. Subjects who do not have resolution of fever will be censored at the time of their last non-missing post-baseline temperature assessment.

Alleviation of symptoms will be determined by assessment of symptoms as reported on each Subject Diary. The time to alleviation of symptoms, defined as the time from initiation of study drug until the start of the 21.5 hour period (24 hours less 10%) where all symptoms of influenza are recorded as none or mild, will be estimated overall and for each age group using the Kaplan-Meier method. Subjects who do not experience alleviation of symptoms will be censored at the date of their last non-missing post-baseline assessment.

Change from baseline in \log_{10} TCID₅₀/mL through Day 3, Day 7, and Day 14 will be presented by age group and overall for subjects with positive viral titers at baseline (\log_{10} TCID₅₀/mL > 0.5). A box plot and a histogram of the TCID₅₀/mL values will be presented by visit and age group. In addition, the median change from baseline in TCID₅₀/mL will be presented by visit and age group.

The number and percent of subjects with positive viral titers at baseline (\log_{10} TCID₅₀/mL > 0.5) that shed virus at each visit will be presented by age group and overall.

The RT-PCR results at each visit will be presented by age group and overall for subjects with positive RT-PCR results at baseline.

Change from baseline to last positive value of influenza virus susceptibility to neuraminidase inhibitors will be assessed using virology laboratory tests. Virology laboratory tests will include phenotypic characterizations of influenza virus recovered (hemagglutinin and neuraminidase) and viral susceptibility to zanamivir, oseltamivir, and peramivir, as well as genotyping of virus isolates. These analyses will be presented overall and by age group and viral subtype.

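### The documents disagree on when diary temperature recording ends, and under one version a subject with normal temperature who is still taking antipyretics can stop before the fever endpoint can be met and be informatively censored

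*Protocol*

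**What the plan says.** Three versions of the recording rule appear.

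- **Diary training, Protocol 10.1.2.2.** Temperature is "obtained at approximately 12-hour intervals each day until the temperature normalizes for 48 hours". The only antipyretic condition in that bullet is one of timing: "4 hours from last antipyretic medication administration or immediately prior to administration".
- **Protocol Synopsis (Methodology), Protocol Table 1 footnote 3, Protocol 10.1, SAP 1.1 and SAP 1.2 footnote 3.** Recording ends after 48 normal hours, explained in Table 1 as "temperature without antipyretic is < 37.4°C/ 99.4°F orally for 4 measurements". None of these places says how many hours off antipyretic are meant. The Synopsis, Protocol 10.1 and SAP 1.1 follow the stop rule with the same 4-hour or just-before-dose timing condition.
- **Protocol 10.2.1, the section on body temperature.** Subjects "record oral body temperatures approximately every 12 hours through Day 14 in the subject diary". No early stop is given.

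Protocol 9.9.1 permits antipyretics without stating a limit on frequency. It makes the timing condition one of best effort: "temperature measurements recorded by the subjects will be taken, whenever possible, at least 4 hours after administration of the antipyretic medication".

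The endpoint is stricter. Protocol 13.8.2, SAP 3.3.8 and SAP 5.2.2 require an oral temperature below 37.4°C/99.4°F, and that "no antipyretic medications have been taken for at least 12 hours". SAP 3.3.8 takes this from the subject diaries. SAP 5.2.2 adds: "Subjects who do not have resolution of fever will be censored at the time of their last non-missing post-baseline temperature assessment".

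**The concern.** The condition for stopping (4 hours) and the condition for an event (12 hours) are not linked anywhere. If a site follows the diary-training text, a subject can satisfy the stop rule without ever having had a reading that could count as an event. Clinic temperatures cannot fill the gap, because the endpoint is built from the diary.

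The censoring is then triggered by the temperature becoming normal while antipyretics continue, so it is related to the outcome. Kaplan-Meier assumes that it is not. The affected outputs are the fever tables (overall and by viral subtype), the Kaplan-Meier plot, the median with confidence interval and the box plots listed in SAP Section 9.

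**Working it through.** The plan gives no figure to reproduce: the sample size is not statistically derived and nothing is tested. Two checks apply. All dosing patterns, shares and fever times below are assumptions, because the documents give none.

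**1. Can a subject stop without qualifying?** Take readings at 08:00 and 20:00, with doses just after the 08:00 reading, at 14:00 and at 22:00. The antipyretic-free time is 10 h before the 08:00 reading (22:00 to 08:00) and 6 h before the 20:00 reading (14:00 to 20:00). Both exceed 4 h and neither reaches 12 h. Four such normal readings meet the diary-training stop rule, and none is an event.

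Longest antipyretic-free time at any permitted reading, by pattern:

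| Dosing pattern | Longest gap | Can qualify? |
|---|---|---|
| every 4, 6 or 8 h | 4, 6 or 8 h | no |
| 07:00, 12:00, 17:00, 22:00 | 9 h | no |
| 07:00, 13:00, 19:00, or every 12 h | 12 h | only if read immediately before the dose that ends the 12-h gap |
| once daily | 24 h | yes |

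The problem is therefore confined to subjects whose every dosing gap is under 12 h.

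**2. How much does stopping early change the curve?** Let time to normal temperature T be exponential with median 48 h, rounded up to a 12-h reading grid. A share q take antipyretics with all gaps under 12 h.

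- *Normal temperature, ignoring antipyretics:* the proportion not yet normal is 2^(−t/48).
- *Stop and censor:* affected subjects are censored at the fourth normal reading, T + 3×12 = T + 36 h. With s = 2^(−1/4) = 0.841, the Kaplan-Meier hazard at reading k is (1−s)(1−q)s^(k−1) / [(1−q)s^(k−1) + qR], where R = 1 for k ≤ 4 and s^(k−4) after that. For q = 20%, the product over the six readings to 72 h is 47.3%. From the fourth reading the hazard is constant at 0.112, so the 120 h value is 47.3% × 0.888^4 = 29.4%.
- *Recording continued:* affected subjects stop antipyretics D hours after normalising and have the event at T + D + 12. The proportion unresolved is (1−q)·2^(−t/48) + q·P(T + D + 12 > t). At 72 h the last probability is 1 for both ranges of D, giving 0.8 × 35.4% + 20% = 48.3% for q = 20%.

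Percentage unresolved:

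| Time | Normal temperature | q | Stop and censor | Continued, D 48–96 h | Continued, D 96–168 h |
|---|---|---|---|---|---|
| 72 h | 35.4 | 10% | 41.2 | 41.8 | 41.8 |
| 72 h | 35.4 | 20% | 47.3 | 48.3 | 48.3 |
| 120 h | 17.7 | 10% | 23.2 | 22.5 | 25.9 |
| 120 h | 17.7 | 20% | 29.4 | 27.4 | 34.1 |
| 168 h | 8.8 | 10% | 13.0 | 11.3 | 15.7 |
| 168 h | 8.8 | 20% | 18.3 | 13.7 | 22.5 |

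At 72 h, stopping changes the estimate by 0.6 to 1.0 points. At 120 h and 168 h the difference runs from about 5 points too low to about 5 points too high, depending on how long antipyretics continue.

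Medians show the same. With a true median of 36 h and D of 48–96 h (no grid), stop-and-censor against continued recording gives 42 v 42 h at 10% affected, 50 v 51 h at 20%, and 61 v 65 h at 30%.

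**The case against.** The strongest reply is that the early stop is not settled. Protocol 10.2.1, the section devoted to the measurement, runs recording through Day 14, and under it the event can still be observed once antipyretics end. The off-antipyretic wording appears in five places across both documents. On a plain reading, it keeps on-antipyretic values from counting towards the stop at all. The parenthesis in Protocol 10.1.2.2 may be only a measurement-timing rule. All of this stands, and it rules out saying that the plan makes the event unobservable. It does not remove the problem. Sites hold three rules, the training text is one of them, and the off-antipyretic phrase has no interval attached. The SAP 5.4 statement that the SAP prevails over the protocol settles the analysis, not what subjects wrote down.

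A reader might also infer that regular antipyretic users never qualify. The dosing table shows otherwise: once-daily use qualifies, and 12-hourly or three-times-daily use can.

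A reader might further attribute to the stop rule the gap at 72 h between 35% for normal temperature and 41% to 47% for the Kaplan-Meier estimate. Continued recording gives 42% to 48%, so that gap comes from requiring 12 antipyretic-free hours, which is a legitimate choice of endpoint.

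Finally, the SAP already summarises antipyretic doses by study day and lists temperatures and symptom-relief medication, so affected subjects can be traced. That makes the repair easy, but no planned output counts them.

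**Conclusion.** The conflict over recording duration is real, and so is the mismatch between the 4-hour and 12-hour conditions. Under the diary-training wording, a subject with normal temperature whose dosing gaps are all under 12 h can stop recording before any reading qualifies. The resulting censoring is informative.

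The size and direction of the bias on the antipyretic-free endpoint cannot be determined from the documents. They give neither the share of subjects affected nor how long antipyretic use lasts. Under the assumptions above, the effect is near zero at 72 h and a few percentage points, of either sign, from about 120 h. It would be tempting to say that the elderly curve is distorted more than the younger one, but nothing in the documents shows that antipyretic use differs by age.

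The endpoint is secondary and descriptive, and the primary safety endpoint is untouched. The point is worth correcting because the correction is cheap, not because a main conclusion depends on it.

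**What to change.** Reconcile the Protocol Synopsis, Table 1, Sections 10.1, 10.1.2.2 and 10.2.1, and SAP 1.1 and 1.2 to one recording rule. Diary temperatures should continue at least until a normal reading meets the 12-hour antipyretic-free condition, or through Day 14 as Protocol 10.2.1 already says. If a stop rule based on being off antipyretic is kept, state the interval.

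The SAP is dated June 2018 and the protocol estimated last-subject completion in April 2018, so the diaries may already be complete. For data already collected:

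- report, by age group, how many subjects were censored for fever after meeting the 48-hour stop rule;
- add one Kaplan-Meier sensitivity estimate that counts those subjects as events at the first of their four normal readings. Label it as time to normal temperature regardless of antipyretic use, because it answers a different question from the planned endpoint.

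The cost is a wording change, a few more diary entries for subjects still taking antipyretics, and one extra table. The count and the estimate need only diary temperatures and medication times that the protocol already collects.

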#### **10.1.2.3. Day 3**

The following procedures/assessments will be performed on Day 3. The Day 3 assessment will be performed as a clinic visit.

- Measure vital signs (blood pressure, pulse rate, and respiration rate)
- Conduct an assessment for IRC; if an IRC is suspected, then the physical examination will confirm the actual presence or absence of the IRC
- Conduct a targeted physical examination
- Measure oral body temperature
- A serum sample for future influenza antibody analysis
- Review the subject diary for completeness and instruct the subject/caregiver on the need to ensure complete recording of required assessments, if needed.
- Collect a bilateral adequate nasal swab specimen for viral culture, quantitative PCR assay and susceptibility to neuraminidase inhibitors.
- Review and record concomitant medications
- Review and record AEs

#### **10.1.2.4. Day 7**

The following procedures/assessments will be performed on Day 7 (+ 2 days). The Day 7 assessment will be performed as a clinic visit.

- Measure vital signs (blood pressure, pulse rate, and respiration rate)
- Conduct an assessment for IRC; if an IRC is suspected, the physical examination will confirm the actual presence or absence of the IRC
- Conduct a targeted physical examination
- Measure oral body temperature
- Blood specimen collection for clinical chemistry and clinical hematology tests as specified in Sections [11.2.1](#) and [11.2.2](#) and a serum sample for future influenza antibody analysis.
- Collect urine for urinalysis

- Review the subject diary for completeness and instruct the subject/caregiver on the need to ensure complete recording of required assessments, if needed.
- Collect a bilateral adequate nasal swab specimen for viral culture, quantitative PCR assay and susceptibility to neuraminidase inhibitors.
- Review and record concomitant medications
- Review and record AEs

#### **10.1.2.5. Day 14 (End of Study)**

The Day 14 assessments will be performed as a clinic visit. The following procedures/assessments will be performed on Day 14 (+ 3 days) or at the time of early withdrawal, where possible:

- Measure vital signs (blood pressure, pulse rate, and respiration rate)
- Measure and record oral body temperature
- Perform a urine or serum pregnancy test (non-pregnant females of childbearing potential only)
- Conduct an assessment for the presence of possible IRC; if an IRC is suspected, a targeted physical exam should be conducted to confirm the absence or presence of the IRC
- Review the subject diary for completeness
- Collect a bilateral adequate nasal swab specimen for viral culture, quantitative PCR assay and susceptibility to neuraminidase inhibitors.
- Review and record concomitant medications
- If Day 7 labs are, in the opinion of the investigator, significantly abnormal or significantly changed from baseline, collect blood specimen for clinical chemistry and/or clinical hematology tests as specified in Sections [11.2.1](#) and [11.2.2](#) and a serum sample for future influenza antibody analysis.
- If Day 7 urinalysis is, in the opinion of the investigator, significantly abnormal or significantly changed from baseline, collect urine for urinalysis
- Review and record AEs

### **10.2. Clinical assessments of Effectiveness**

Effectiveness will be evaluated through assessments of body temperature, clinical symptoms of influenza, usual daily activities assessments, incidence of influenza-related complications (see Section [10.2.4](#)) for details), influenza virus titers, and changes in viral sensitivity to other antiviral drugs.

#### **10.2.1. Body Temperature**

The Investigator will record oral body temperature at Screening. The baseline temperature will be recorded at the Day 1 visit prior to dosing, regardless of whether the subject had recently taken an antipyretic. Thereafter, the subject or caregiver will record oral body temperatures approximately every 12 hours through Day 14 in the subject diary. Subjects or caregivers will measure their oral temperature with an electronic thermometer (provided by the Sponsor for the study). With the exception of the

baseline measurement, subjects will be instructed to take all temperature measurements at least 4 hours after, or immediately before, administration of oral acetaminophen or other antipyretic medications. The times of each temperature determination will be recorded in the Subject Diary.

### 10.2.2. Influenza Signs and Symptoms

Subjects will be asked to provide an assessment of 7 influenza symptoms (cough, sore throat, nasal congestion, myalgia [aches and pains], headache, feverishness, and fatigue) on a 4-point severity scale (0, absent; 1, mild; 2, moderate; 3, severe) beginning at Screening then twice daily beginning on Day 1 through Day 13, and prior to the subject's clinic visit on Day 14. Once all symptoms are score a 0 or 1 for at least 48 hours the can discontinue recordings. The definitions to be used to assign severity are as follows:

0, Absent	no symptom present (no cough, no sore throat, etc.)
1, Mild	symptom present and slightly uncomfortable
2, Moderate	symptom is very uncomfortable
3, Severe	symptom is intolerable

The subject diary will be reviewed by study staff at each visit for completion of the record of all required items, with particular emphasis on alleviation of clinical symptoms as well as relapse of symptoms. Study staff will not attempt to ask subjects or caregiver to retrospectively complete missing subject diary data for any scheduled assessments that have not been completed prior to the clinic visit. However, study staff should, however, remind the subject or caregiver to complete the subject diary at all scheduled times.

